14.2 Secondary Endpoints

14.2.1 Proportion of Subjects Alive and Not Requiring Supplemental Oxygenation

The proportion of responders is defined as participants who are alive and do not require supplemental oxygenation or ventilatory support (including noninvasive or mechanical ventilation and Extra Corporeal Membrane Oxygenation [ECMO]).

The difference in proportion of each dose to placebo will be derived with two-sided 95% CIs based on the Miettinen-Nurminen method and presented in a tabular and graphical format at the following analysis visits: Day 7, Day 14, Day 21, Day 28, Day 44 and Day 60.

The derivation of response at Day 14 will be based on the Ordinal Scale for Clinical Severity presented in Section 14.2.2 and the same logic will be applied for all the other time points, data collected on the ‘Ordinal Scale for Clinical Severity’ eCRF page, using the following derivation algorithm:

- If clinical status score < 4 on analysis Day 14 then the participant will be considered a responder on Day 14;

- If clinical status ≥ 4 on analysis Day 14 then the participant will be considered a non-responder on that day.

The rules below to define responder status in special cases will be followed:

| # | Situation | Outcome |
|---|----------------------------|---------------|
| 1 | Death on or before Day 28 | Non-responder |
| 2 | Missing on analysis Day 14 | Missing |

Number and percentage of subjects with response at each analysis visit and the corresponding two-sided Wilson 95% CI will be presented.

In addition, summary score estimates of the common difference in proportion, stratified for corticosteroids use in the 48h prior to randomization and country will be presented with 95% CIs based on stratified Newcombe confidence limits for the differences in proportions (Kim, 2013).

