To evaluate the change in clinical status with M5049 compared to placebo.	Clinical status from Day 1 through Day 60 (on a 9-point ordinal scale): 
 0. Uninfected: no clinical or virological evidence of infection. 1. Ambulatory: no limitation of activities. 2. Ambulatory: limitation of activities. 3. Hospitalized, mild disease: hospitalized, no oxygen therapy. 4. Hospitalized, mild disease: oxygen by mask or nasal prongs. 5. Hospitalized, severe disease: noninvasive ventilation or high flow-oxygen. 6. Hospitalized, severe disease: intubation and mechanical ventilation. 7. Hospitalized, severe disease: ventilation + additional organ support – e.g., pressors, RRT, ECMO. 8. Death.
To assess the PK of M5049.	Pharmacokinetic parameters: C_{max} , t_{max} , λ_z , $t_{1/2}$, AUC_{0-last} , AUC_{0-12h} , $AUC_{0-\infty}$, CL/F , V_z/F , C_{max}/D , AUC_{0-last}/D , AUC_{0-12h}/D , $AUC_{0-\infty}/D$, $R_{acc}(AUC_{0-12h})$, and $R_{acc}(C_{max})$ on Day 1 and Day 7.

AESI = adverse event of special interest; CL/F = apparent total body clearance of study intervention following extravascular administration; ECG = electrocardiogram; ECMO = extracorporeal membrane oxygenation; ICU = intensive care unit; PK = pharmacokinetic; R_{acc} = accumulation ratio; RRT = rapid response team; SAE = serious adverse event; TEAE = treatment-emergent adverse event; V_z/F = apparent volume of distribution.

Part B Objectives

OBJECTIVES	ENDPOINTS (OUTCOME MEASURES)
Primary Efficacy	
To evaluate the time to recovery in participants hospitalized due to COVID-19 pneumonia with M5049 compared to placebo.	Time to recovery from Day 1 through Day 28, defined as time from Day 1 to first occurrence of WHO 9-point ordinal scale 3 or less.
Primary Safety	
To assess the safety of M5049 compared to placebo.	
 • Incidence of TEAEs, AESIs, TEAEs leading to treatment discontinuation, and SAEs from Day 1 through Day 60. • Clinically significant changes in laboratory parameters and ECGs from Day 1 through Day 28.
Secondary	
To assess the proportion of participants free of respiratory support with M5049 compared to placebo.	Alive and not requiring supplemental oxygenation (including any supplemental oxygen, noninvasive or mechanical ventilation and ECMO) through Day 28.

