Concomitant medication/procedure review		←-----Once daily during hospitalization. If discharged, then at study visits (e.g., Days 3, 5, 7, 10, 14, 21, 28, 44, and 60)-----→												Document what is available from the participant's chart. Record each day at approximately the same time throughout hospitalization; if participant is discharged, either via telemedicine contact or by return to study site at the times indicated only.	

Assessments and Procedures	SCR	Intervention Period (Days)							Continued Surveillance		Safety Follow-up			Relapse Admission ^a	Notes
									HD/ET	EoT					
Study Day		1	2	3	5	7	10		14	21	28	44	60	5 to 60	
Visit Window		± 6 h		± 12 h		± 24 h			+ 2 days	± 5 days	± 7 days	± 6 h			
Complete physical examination	X	X						X	X					X	Data may be collected from chart but must be verified by Clinical Investigator.
Brief physical examination			X		X	X	X			X	X				Data may be collected from the chart but must be verified by a Clinical Investigator (unless participant is discharged).
Vital signs, weight, height		←---Once daily during hospitalization (incl. predose on Day 1). --> If discharged, then at study visits (e.g., Days 3, 5, 7, 10, 14, 21, and 28)									X	X	X		Vital signs: body temperature, blood pressure, respiration rate, pulse (unless participant is discharged). Weight will be recorded at Screening, relapse admission, and Day 28 (if feasible). Height will be recorded at Screening only. Record each day at approximately the same time throughout hospitalization. All data collected from the chart. After discharge, record only at times indicated if/when participant returns to study site.
SpO ₂ saturation and FIO ₂ (or liters of O ₂)		←---Once daily during hospitalization (incl. predose on Day 1). --> If discharged, then at study visits (e.g., Days 3, 5, 7, 10, 14, 21, and 28)												X	SpO ₂ measured by pulse oximetry; record each day at approximately the same time of day throughout hospitalization and after discharge, at times indicated only if participant returns to study site (refer to Section 5).
SpO ₂ saturation in room air for 24 hours		←-----Record SpO ₂ measures after the first SpO ₂ ≥ 94% in room air during hospitalization----->												X	At any time prior to hospital discharge when SpO ₂ ≥ 94% in room air for the first time, document if participant maintains this status 24 hours later (unless participant is discharged).

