14.2.2 Clinical Status

Clinical status will be based on data collected on the ‘Ordinal Scale for Clinical Status’ eCRF page and is assessed with the following ordinal scale:

0. Uninfected: no clinical or virological evidence of infection.
1. Ambulatory: no limitation of activities.
2. Ambulatory: limitation of activities.
3. Hospitalized, mild disease: hospitalized, no oxygen therapy.
4. Hospitalized, mild disease: oxygen by mask or nasal prongs.
5. Hospitalized, severe disease: noninvasive ventilation or high-flow oxygen.
6. Hospitalized, severe disease: intubation and mechanical ventilation.
7. Hospitalized, severe disease: ventilation + additional organ support – e.g., pressors, RRT, ECMO
8. Death.

In case of death, the participant will be counted with the clinical status =8 (death) for any scheduled timepoint after death date. There will be no imputation of missing data.

Clinical status is expected every day during hospitalization and then at every scheduled visit after discharge. Day 1 assessment will serve as baseline measurement. If missing, the last non-missing measurement prior to randomization will be used.

The number and percentage of participants in each clinical status category as well as summary statistics for absolute and change from baseline status will be presented by treatment group, in a tabular and graphical form, using a stacked bar chart.

A cumulative logit model will be used to compare the clinical status results of each M5049 group versus placebo at the following analysis visits: Day 7, Day 14, Day 21, Day 28, Day 44 and Day 60 according to the ordinal scale described above. Under the assumption of proportional odds, the odds ratio (OR) and its 95% Wald CI will be estimated for each M5049 group versus placebo. A score test for the proportional odds assumptions will be reported.

Should the model fail, due to an insufficient number of observations per category of the dependent variable, then relevant categories may be collapsed.

In addition, the following dichotomized versions of the clinical status will be derived, only if at least 6 participants in each level are present:

- Death (clinical status = 8) versus any other category (clinical status \neq 8)
- Worsening (clinical status \geq 5) versus stable/improvement (clinical status $<$ 5)
- In-hospital (clinical status \geq 3) versus hospital discharged (clinical status $<$ 3).

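### SAP 14.2.1 derives freedom from supplemental oxygen from ordinal score < 4 alone, so a participant discharged on home oxygen would probably count as a responder, contrary to the protocol endpoint

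*SAP*

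**What the plan says.** The protocol lists this Part B secondary endpoint in 1.1 Synopsis and 3.2: "Alive and not requiring supplemental oxygenation (including any supplemental oxygen, noninvasive or mechanical ventilation and ECMO) through Day 28". SAP 14.2.1 keeps that meaning in its opening definition, where responders are "participants who are alive and do not require supplemental oxygenation or ventilatory support".

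The derivation that follows uses one source, the eCRF page for the ordinal scale, and one cut-off: "If clinical status score < 4 on analysis Day 14 then the participant will be considered a responder on Day 14". A score of 4 or more is a non-responder, and "the same logic will be applied for all the other time points", so the rule governs Days 7, 14, 21, 28, 44 and 60. Two special cases are listed. "Death on or before Day 28" gives a non-responder, and a missing score leaves the response missing. Oxygen after discharge is not addressed.

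SAP 14.2.2 sets out the scale. The lowest category that records oxygen use is 4, "Hospitalized, mild disease: oxygen by mask or nasal prongs". Score 2 is "Ambulatory: limitation of activities", and score 1 is its counterpart without limitation.

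After discharge, Protocol 1.2 schedules the ordinal score and the concomitant medication/procedure review at visits to Day 60, on site or by telemedicine. SpO2 with FiO2 or litre flow is recorded "throughout hospitalization and after discharge, at times indicated only if participant returns to study site", with routine visits listed only to Day 28.

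**The concern.** The endpoint's definition and its derivation do not identify the same participants. The scale separates oxygen from no oxygen only for people still in hospital. Once a participant goes home, the score describes activity, and oxygen use drops out of the derivation.

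SAP 14.2.1 reports between-arm differences with confidence intervals at six visits. Protocol 4.7 expects most participants to have been discharged by Day 28, so the group for whom the score says nothing about oxygen grows over those visits. The endpoint also still carries weight: Protocol 2.1 and 4.1 continue to describe the Day 14 status on this outcome as what the study evaluates.

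**Working it through.** The documents give no sample size, power or expected rate for this endpoint, so there is no plan figure to reproduce. The check is first one of logic, then an illustration of size.

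**Logic**

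1. Categories 4 to 7, the only ones that record oxygen or ventilation in use, are all restricted to hospitalized participants (SAP 14.2.2).
2. SAP 14.2.2 itself treats a status below 3 as discharged, whatever the oxygen use.
3. A discharged participant on home oxygen therefore has no oxygen category to fall into, and the likely score is 1 or 2. This is an inference from the scale wording.
4. Since 1 and 2 are both below 4, SAP 14.2.1 makes this participant a responder. Under the protocol definition the same participant is a non-responder.

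**Can the case arise?** Yes. Inclusion Criterion 6 and the note to Exclusion Criterion 4d admit people on chronic oxygen of up to 2 L. Such a participant could score 4 in hospital and 1 or 2 at home on the same flow, changing from non-responder to responder through discharge alone. Discharge on room air is not required either. Protocol 4.8 defines relapse only for those discharged with sustained room-air saturation of at least 94%, which implies that others may leave without it.

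**Is there a check elsewhere?** SAP 14.2.3 requires room air for the SpO2 endpoint and uses the pulse oximetry and respiratory status pages. SAP 14.2.1 has no equivalent, and the SAP modification history keeps sensitivity analysis for the primary endpoint only.

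**Size (illustration)**

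Inputs: 150 participants randomized 1:1:1 (Protocol 4.1), so n = 150/3 = 50 per arm. Assumed, not in the documents: share discharged at Day 14, d = 60%; share of those on home oxygen, h = 0 to 20%.

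Overstatement of the responder rate = d × h; participants miscounted per arm = n × d × h.

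| d | h | Overstatement (points) | Miscounted of 50 |
|---|---|---|---|
| 60% | 0% | 0 | 0 |
| 60% | 5% | 3 | 1.5 |
| 60% | 10% | 6 | 3 |
| 60% | 20% | 12 | 6 |
| 80% | 20% | 16 | 8 |

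The last row shows the effect of a higher discharge share.

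**Between-arm difference.** Scored difference = true difference + (miscounted share on active − miscounted share on placebo), each as a share of the whole arm. Assume true oxygen-free rates of 60% on placebo and 75% on active, a difference of 15 points.

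| Miscounted, placebo | Miscounted, active | Scored rates | Scored difference |
|---|---|---|---|
| 10 | 10 | 70% v 85% | 15 |
| 15 | 5 | 75% v 80% | 5 |
| 5 | 15 | 65% v 90% | 25 |

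Equal shares raise both rates and leave the difference unchanged. Unequal shares shrink or enlarge it.

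**The case against.** The strongest reply is that use of the scale was deliberate. The amendment rationale says the former primary endpoint came from the same WHO scale. Room-air oxygenation has its own secondary endpoint in SAP 14.2.3, and SAP section 9 treats all tests as exploratory. How sites score home oxygen is not documented, every rate above is assumed, and the trial is double-blind, which makes a large imbalance in home-oxygen use less likely. With 50 per arm and rates near 60%, the 95% confidence interval for a difference has a half-width of about 19 points (1.96 × √(2 × 0.6 × 0.4 / 50) = 0.19), so a 6-point shift is small beside it.

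Most of this stands as a limit on size. It does not reconcile the rule with the definition, since a deliberate use of the scale still leaves an endpoint that says one thing and measures another. Blinding does not settle the matter either. If treatment changes when people are discharged, the share of an arm at home on oxygen on a fixed day can differ without any unblinding.

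A reader might infer three stronger things that the documents do not support:

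- **The endpoint merely measures discharge.** It does not. Scores 3 and 4 separate inpatients off and on oxygen correctly, someone readmitted on oxygen scores at least 4, and discharge is analysed separately.
- **Oxygen data exist at every contact and are ignored.** After discharge, SpO2 and FiO2 depend on an on-site return and are scheduled to Day 28. Protocol 9.1.2 takes the method of respiratory support from the hospital chart. Only the concomitant medication/procedure review reaches remote contacts to Day 60.
- **The rule favours M5049.** The direction of any bias is unknown, and there is none in the difference if the share at home on oxygen is equal across arms.

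**Conclusion.** The mismatch is established from readable text: the rule in SAP 14.2.1 cannot detect oxygen use after discharge, and the protocol endpoint excludes it. That such a participant is scored 1 or 2 is likely but inferred. With 60% discharged by Day 14 and 0 to 20% of those on home oxygen, the responder rate is overstated by 0 to 12 points. Both inputs are assumptions, and the answer is zero if nobody goes home on oxygen. Bias in the treatment difference requires unequal home-oxygen use between arms and could go either way.

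The primary endpoint also turns on a score of 3 or less, and a reader might extend the criticism to it. That endpoint is defined directly by the scale, so it does not contradict its own definition.

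For a secondary endpoint in an exploratory trial, this is a correction that should be made, not one on which the trial's main result depends.

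**What to change.** In SAP 14.2.1, define a responder at an analysis visit as alive, score below 4, and with no supplemental oxygen recorded for that visit. The sources are the concomitant medication/procedure review, already done at every contact to Day 60 (Protocol 7.4 requires nondrug interventions to be recorded), together with the SpO2/FiO2 and respiratory status pages where available.

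Ask one yes/no question on current oxygen use at every remaining post-discharge contact, on site or remote. Asking it the same way everywhere matters: if on-site pages were used with the score alone as fallback, the same participant could be a non-responder when seen and a responder when telephoned.

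State how participants on chronic baseline oxygen are classified; otherwise those who stay on their usual oxygen can never respond. Report the score-below-4 version alongside as a sensitivity analysis, with known post-discharge oxygen use by arm. Where oxygen use after discharge is unknown, label the result as score below 4.

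The cost is SAP wording plus one data item added mid-trial. SAP 6.1 and 6.2 describe the first and later IDMC meetings as already held, so the question cannot cover visits already completed. For those, only the existing records are available.

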10.4.3 Analysis of the Secondary Endpoints

10.4.3.1 Analysis of Alive and Not Requiring Supplemental Oxygenation through Day 28

The number and proportion of participants alive and do not require supplemental oxygenation or ventilatory support (including mechanical ventilation and ECMO) will be described at Day 7, Day 14, and at regular intervals.

The difference of each dose versus placebo in proportion of participants who are alive and do not require supplemental oxygenation or ventilatory support on Day 7, on Day 14 and on Day 28 will

be provided graphically together with two-sided 95% CIs. The CIs will be based on the Miettinen & Nurminen method (Miettinen 1985).

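### The death rule for the responder endpoint has a fixed Day 28 cutoff, so on a literal reading a later death cancels a response at Day 14, and by extension at Days 7 and 21

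*SAP*

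**What the plan says.** SAP 14.2.1 reports the responder proportion and its difference from placebo, "presented in a tabular and graphical format at the following analysis visits: Day 7, Day 14, Day 21, Day 28, Day 44 and Day 60". Only one visit is spelled out: "If clinical status score < 4 on analysis Day 14 then the participant will be considered a responder on Day 14". A score of 4 or more makes the participant a non-responder on that day. For the remaining visits, "the same logic will be applied for all the other time points".

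A short table follows, introduced by "The rules below to define responder status in special cases will be followed". It has two rows:

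- "Death on or before Day 28" gives non-responder.
- "Missing on analysis Day 14" gives missing.

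The second row is anchored to the Day 14 visit. The first is not anchored to any visit.

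SAP 14.2.2, which uses the same ordinal scale, handles death differently: "the participant will be counted with the clinical status =8 (death) for any scheduled timepoint after death date". Protocol 10.4.3.1 specifies the comparison for participants who are "alive and do not require supplemental oxygenation or ventilatory support on Day 7, on Day 14 and on Day 28". SAP section 7, which lists departures from the protocol analyses, mentions only the choice of stratification factors.

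**The concern.** A rate labelled Day 14 should describe participants' state at Day 14. With a cutoff fixed at Day 28, it also depends on deaths up to two weeks later. The response table and the clinical-status table would then disagree about the same participant at the same visit: a score below 4 in one, a non-responder in the other.

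At stake are the labelling and interpretation of the Day 7, 14 and 21 response rates, and possibly their differences from placebo. Day 14 matters most. Status at Day 14 was the primary efficacy endpoint before the amendment, and protocol 2.1 and 4.1 still describe the study in those terms.

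**Working it through.** The documents give no rate or event count for this rule, so there is no figure of theirs to reproduce. The check has two parts: the logic of the rule, then the size of its effect.

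**Logic.** Take a participant whose score is 2 at every assessment before death. Compare two classifications at each visit:

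- On-the-day: score 8 once death precedes the visit (SAP 14.2.2), otherwise the observed score; below 4 is a responder (R), 4 or more a non-responder (NR).
- Literal rule: NR at every visit if death occurs by Day 28, otherwise as on-the-day.

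| Visit | Death Day 5 | Day 10 | Day 20 | Day 27 | Day 35 | Day 50 |
|---|---|---|---|---|---|---|
| 7 | both NR | **differ** | **differ** | **differ** | both R | both R |
| 14 | both NR | both NR | **differ** | **differ** | both R | both R |
| 21 | both NR | both NR | both NR | **differ** | both R | both R |
| 28 | both NR | both NR | both NR | both NR | both R | both R |
| 44 | both NR | both NR | both NR | both NR | both NR | both R |
| 60 | both NR | both NR | both NR | both NR | both NR | both NR |

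Wherever they differ, on-the-day status is R and the literal rule gives NR. This happens only when death falls after the visit and by Day 28. For Day 14 the result follows directly from the text. For Days 7 and 21 it relies on the sentence extending the logic to other visits.

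**Effect per participant.** Protocol 4.1 plans 150 participants randomized 1:1:1, so 150/3 = 50 per arm. One reclassified participant moves an arm's rate by 1/50 = 2.0 percentage points. As an illustration, assume 25/50 = 50% responders on the day (Wilson 95% CI 36.6% to 63.4%):

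| Responders who die later, by Day 28 | Rate under literal rule | Wilson 95% CI |
|---|---|---|
| 1 | 24/50 = 48% | 34.8% to 61.5% |
| 2 | 23/50 = 46% | 33.0% to 59.6% |
| 3 | 22/50 = 44% | 31.2% to 57.7% |

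**How many participants.** This part is assumption only. The share reclassified at Day 14 is 28-day mortality × share of those deaths after Day 14 × share of those participants off oxygen at Day 14.

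- Low: 0.05 × 0.4 × 0.1 = 0.2%, or 0.1 of 50.
- Middle: 0.10 × 0.5 × 0.2 = 1.0%, or 0.5 of 50.
- High: 0.15 × 0.6 × 0.3 = 2.7%, or 1.35 of 50.

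The high end takes all three factors at their upper value. No corresponding figure was worked out for Day 7 or Day 21.

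**The case against.** The strongest defence is that the rule is a deliberate composite. The endpoint tables in protocol 3.2 and SAP 5.2 describe the endpoint as running through Day 28. The time-to-event rules in SAP 14.1.1, 14.2.3 and 14.2.9 also count a later death against the participant. The tension in the wording is real, but it does not rescue the row. Response is still scored visit by visit, and a Day 26 death would cancel a Day 14 response while a Day 30 death would not. The time-to-event rules use a different cutoff for death (Day 60 or study completion) and give one outcome per participant rather than a status at each visit.

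A second defence is that extending the same logic means moving the death cutoff to each visit. That is possible for Days 7 and 21. It does not help at Day 14, where the worked derivation itself carries the Day 28 cutoff.

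Third, 14.2.1 and 14.2.2 define separate endpoints, so a difference between them is not in itself a contradiction. That is fair. Moreover, the status tables in 14.2.2 let a reader add up scores 0 to 3 and largely recover the on-the-day rate.

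A reader might also infer that the row serves no purpose because 14.2.2 already handles deaths. The documents do not support that. Section 14.2.2 assigns score 8 only after the death date, whereas the row also covers a death on the Day 28 visit date itself. It may also settle participants with no score at the visit, although the order of the two rows is not stated.

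**Conclusion.** The death row does not match the per-visit endpoint it serves. At Day 14 this is so on the plain text; at Days 7 and 21 it follows if the same logic is taken literally. Days 28, 44 and 60 are essentially unaffected. The row conflicts with protocol 10.4.3.1, and SAP section 7 declares no departure.

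The practical effect is probably small: about 2 points in an arm's rate per affected participant, and between 0.1 and about 1.4 participants per arm of 50 at Day 14 under assumptions that come from outside the documents. A reader might infer that the comparison with placebo is biased. That does not follow: the difference shifts only if such deaths are imbalanced between arms, and nothing in the documents indicates that they would be. The primary time-to-recovery analysis does not use this row, and SAP section 9 treats all tests as exploratory. The point is worth correcting because the rates would otherwise not be what their labels say.

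**What to change.** Replace the row in SAP 14.2.1 with: death on or before the analysis visit is non-response at that visit, including when the score at that visit is missing. Apply it separately at Days 7, 14, 21, 28, 44 and 60.

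State which date defines the visit. Under SAP 9.9, analysis Day 14 covers Days 12 to 17, so a death on Day 16 is unresolved until the text says whether the target day or the assessment date used within the window applies. Generalize the missing-data row from Day 14 to each analysis visit in the same edit.

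If survival through Day 28 is also wanted as part of a composite, define and label it as a separate endpoint, and reconcile it with the wording in protocol 3.2 and SAP 5.2.

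The cost is a sentence or two in the SAP and the matching change in the derivation of the responder flag. No new data are needed, and the sample size and primary analysis do not change.
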